9 STATISTICAL CONSIDERATIONS

9.1 Statistical Hypotheses

Not applicable.

9.2 Sample Size Determination

Approximately 24 participants will be enrolled to complete at least 18 participants. Participants who discontinue early from the study may be replaced at the discretion of the sponsor. No formal sample size calculation is performed as this is not a statistically powered study. The number of participants is based on the precedent set by other studies of similar nature. The number of participants planned is considered sufficient to achieve the study objectives.

Based on data from Study 8062-CL-0005, the intrasubject coefficient of variation (CV) for pharmacokinetic parameters AUC_{inf} and C_{max} of ASP8062 are estimated to be between 10% and 24%. Based on the literature, the intrasubject CV for pharmacokinetic parameter C_{max} of morphine is estimated to be 27% [Center for Drug Evaluation and Research, 2008].

Assuming the underlying variability is similar to 27% and the true underlying ratio is 100%, the 90% CI will lie within (76, 131) with > 80% probability.

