6.3.6.2 Randomization

Prior to dosing, participants will be assigned a randomization number in accordance with the randomization code generated by the sponsor's Data Science department or designee.

Participants will be randomized in a 2:1 ratio to ASP8062 or placebo.

Once a randomization number has been allocated to a participant, it will not be assigned to another participant. If a participant withdraws prematurely from the study and is replaced

under the direction of the sponsor, then a replacement randomization number will be assigned. A replacement randomization code will be generated such that replacement participants are assigned to the same treatment as the discontinued participant.

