9.4.4.3 Statistical Analysis of Pharmacokinetic Parameters

To assess the effect of morphine on the pharmacokinetics of ASP8062 and its metabolites (AS3486189, AS3486191 and AS3486192), an analysis of variance (ANOVA) model with treatment (ASP8062 in combination with morphine and ASP8062 alone) as a fixed effect and participants as a random effect will be fitted on natural logarithmic-transformed AUC_{24} and C_{max} . Within the ANOVA, the least squares (LS) mean differences between ASP8062 in combination with morphine and ASP8062 alone, along with 90% CIs for the differences will be estimated. The LS means for AUC_{24} and C_{max} will be back-transformed to produce the geometric LS means and presented with the number of participants for each treatment. The geometric LS mean ratios and their corresponding 90% CIs for each pharmacokinetic parameter will be presented by back-transforming and expressed as percentages.

To assess the effect of ASP8062 on the pharmacokinetics of morphine and its metabolites (M3G and M6G), similar analysis will be done with treatment (morphine in combination with ASP8062 and morphine in combination with placebo) as a fixed effect and participant as a random effect.

If all participants did not complete treatment, then the above analyses will be repeated using an ANOVA with fixed effects for treatment and participant; this analysis will only include participants with complete data in all treatments.

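### The precision stated in section 9.2 needs 18 within-participant pairs, which no comparison in this 2:1 design has; for morphine the probability is 27% to 49% at best, not above 80%

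*Combined protocol and SAP*

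**What the plan says.** Section 9.2 (Sample Size Determination) plans about 24 enrolled participants so that at least 18 complete. It says that no formal calculation was done and that the number follows precedent. It then gives one precision statement: when the variability is close to 27% and "the true underlying ratio is 100%, the 90% CI will lie within (76, 131) with > 80% probability". It names neither the comparison nor the number of participants behind it.

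The same section gives the source of the variability: "Based on the literature, the intrasubject CV for pharmacokinetic parameter C_{max} of morphine is estimated to be 27" per cent. For ASP8062 it gives intrasubject CVs for AUCinf and Cmax that "are estimated to be between 10% and 24" per cent.

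The design is set out elsewhere. Section 6.3.6.2: "Participants will be randomized in a 2:1 ratio to ASP8062 or placebo". Section 4.1 gives every participant a single morphine dose, on day 10. Section 9.4.4.3 plans two sets of comparisons:

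- ASP8062 and its metabolites: ASP8062 with morphine against ASP8062 alone.
- Morphine, M3G and M6G: "similar analysis will be done with treatment (morphine in combination with ASP8062 and morphine in combination with placebo").

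**The concern.** An intrasubject CV describes precision only when each participant is measured under both conditions. Morphine is the drug to which the 27% belongs, but nobody receives it twice. The morphine contrast is therefore between different people, in unequal groups, and carries between-participant as well as within-participant variability. The ASP8062 contrast is within participants, but only the ASP8062 arm contributes to it.

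The sentence is the only quantitative support in section 9.2 for the claim that the planned number is enough for the objectives. The secondary objective is the pharmacokinetic interaction. A reader who relies on the sentence would expect a morphine interval inside roughly 76 to 131. An interval much wider than that could be taken as a surprise or a signal, when it is a known consequence of the design.

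**Working it through.** **Inputs**

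- Interval: two-sided 90%; limits 76% and 131%; true ratio 100%; CV 27% (section 9.2).
- Completers: 18 at minimum, 24 if all complete (section 9.2).
- Allocation 2:1 (section 6.3.6.2), hence 12:6 of 18 or 16:8 of 24. That 18 completers keep the 2:1 ratio is an assumption.
- ASP8062 intrasubject CV: 10% to 24% (section 9.2).
- Total (between-participant) CV for morphine: not given in the documents; a range is shown below.

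**Formulae**

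- Log-scale SD: s = sqrt(ln(1 + CV²)) = sqrt(ln(1 + 0.27²)) = 0.2653.
- Limits on the log scale: ln 0.76 = −0.2744 and ln 1.31 = 0.2700.
- Paired, n participants: SE = s·sqrt(2/n), df = n − 1.
- Parallel, a versus b: SE = s·sqrt(1/a + 1/b), df = a + b − 2.
- Target: P(d − t·se > ln 0.76 and d + t·se < ln 1.31), where d ~ N(0, SE²), se is the estimated standard error (its square distributed as SE²·chi-square/df), and t is the 95th percentile of t on df. The probability is integrated over the distribution of se.

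**The plan's own figure.** With 18 pairs, SE = 0.2653 × sqrt(2/18) = 0.0884 and t(17) = 1.740, so a typical half-width is 0.154. The exact probability is 0.809. Solving for exactly 80% gives limits of (76.4, 131.0), which match the stated (76, 131). With 17 pairs the probability is 0.776. The sentence therefore appears to treat all 18 completers as pairs.

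**Morphine as designed (parallel), with 27% used as the total CV**

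- 12 versus 6: SE = 0.2653 × sqrt(1/12 + 1/6) = 0.1326; t(16) = 1.746; typical half-width 1.746 × 0.1326 = 0.232. The point estimate then has only 0.270 − 0.232 = 0.038 of room on the upper side, about 0.3 SE. Exact probability 0.269.
- 16 versus 8: SE = 0.2653 × sqrt(1/16 + 1/8) = 0.1149; t(22) = 1.717; typical half-width 0.197. Exact probability 0.486.

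**ASP8062 as designed (paired, ASP8062 arm only)**

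- CV 27%: 0.526 with 12 pairs and 0.739 with 16.
- CV 24%: 0.680 with 12 pairs and 0.855 with 16.
- CV 10%: 1.00 with either.

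| Comparison | CV used | Probability within (76, 131) | Limits that reach 80% |
|---|---|---|---|
| Implied: 18 pairs | 27% | 0.809 | (76, 131) |
| Morphine, 12 vs 6 | 27% | 0.269 | (67, 150) |
| Morphine, 16 vs 8 | 27% | 0.486 | (71, 141) |
| ASP8062, 12 pairs | 27% | 0.526 | (71, 140) |
| ASP8062, 16 pairs | 27% | 0.739 | (75, 133) |

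A simulation of 1,000,000 draws gave 0.810, 0.269, 0.486, 0.526 and 0.739 in the same order.

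**Morphine with a larger total CV (assumed values)**

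| Total CV | 12 vs 6 | 16 vs 8 |
|---|---|---|
| 30% | 0.157 | 0.337 |
| 35% | 0.056 | 0.153 |
| 40% | 0.018 | 0.057 |
| 50% | 0.002 | 0.006 |

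At 40% with 12 versus 6, the limits that reach 80% are (55, 180).

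**The case against.** **The study is declared not to be powered.** Section 9.1 has no hypotheses, section 9.2 rests the number on precedent, the primary objective is safety, and no decision rule uses (76, 131). All of this is true. It limits the consequence to the precision statement for a secondary objective, but it does not make a printed probability correct.

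**The sentence may concern ASP8062, where precision is adequate.** This is partly right. At ASP8062's own CV, 16 pairs give at least 0.855. Twelve pairs give 0.868 at a CV of 20% and fall below 0.80 only near the top of the range (0.780 at 22%, 0.680 at 24%). The practical shortfall therefore lies mainly with morphine and its metabolites. The sentence, however, is conditional on 27%, and at that value neither 12 nor 16 pairs reach 0.80.

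**The sentence may concern only the width of the interval.** If the half-width alone had to be below ln 1.31, 12 versus 6 at 27% would give 0.849 and 16 versus 8 would give 0.992. But the text speaks of the true ratio and of the interval lying inside limits. On this reading the 80% limits for 12 versus 6 are (77, 130), a poorer match than 18 pairs. It also still requires 27% to be a total CV, which section 9.2 says it is not.

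**Eighteen pairs is a reconstruction.** The plan does not state it, and any larger number of pairs would also satisfy the claim (24 pairs: 0.928), as would two parallel arms of 18 (0.830). None of these is available in this trial.

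**Conclusion.** The concern holds. The stated probability of more than 80% corresponds to 18 or more within-participant pairs at a CV of 27%, and the trial has no such comparison. For morphine the probability is 0.27 with 12 versus 6 and 0.49 with 16 versus 8. These are best cases at each size, because an intrasubject CV is a floor for the total CV that governs a between-arm contrast. If completers do not keep the 2:1 ratio the figure changes again: 13 versus 5 gives 0.21. For ASP8062 the claim fails at the stated 27%, but it is met at that drug's own CV range with 16 pairs and over most of the range with 12.

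The results assume a true ratio of 100%, log-normal data, and, for the parallel comparison, equal variance in both arms. The safety objective and the planned enrolment are unaffected.

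**What to change.** Replace the single precision sentence in section 9.2 with one statement for each comparison:

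- **ASP8062, day 10 against day 9:** 12 to 16 pairs, intrasubject CV 10% to 24%. At 24%, the probability of lying within (76, 131) is 0.68 with 12 pairs and 0.86 with 16.
- **Morphine, M3G and M6G, ASP8062 arm against placebo arm:** parallel groups of 12 versus 6 to 16 versus 8, with a total CV that is sourced or shown as a range. If 27% is kept as the most favourable value, label it so and give the limits that reach 80%: (67, 150) for 12 versus 6 and (71, 141) for 16 versus 8.

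State for each figure whether it assumes 18 or 24 completers, and that the morphine comparison is between participants.

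The cost is one rewritten paragraph and a less favourable stated precision. No participants, visits or samples are added.

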9.3 Populations for Analyses

For each treatment group, the number and percentage of participants will be characterized for all randomized participants and by each population.

The following populations are defined:

Population	Description
Randomized	All participants who are randomized. Participants will be analyzed according to the study treatment to which they are randomized.
SAF	All participants randomly assigned to study IP and who take at least 1 dose of study IP. Participants will be analyzed according to the IP they actually received. The SAF will be used for all summaries and analysis of the safety data.
PKAS	All participants who receive at least 1 dose of IP for which concentration data are available to facilitate derivation of at least 1 primary pharmacokinetic parameter. Inclusion of participants in the PKAS with missing data or major protocol deviations will be considered by the pharmacokineticist on a case-by-case basis. The PKAS will be used for all summaries and analyses of the pharmacokinetic data.

IP: investigational product; PKAS: pharmacokinetic analysis set; SAF: safety analysis set

9.4 Statistical Analyses

9.4.1 General Considerations

In general, data will be summarized with descriptive statistics for continuous endpoints, and frequency and percentage for categorical endpoints, unless otherwise specified. Percentages by categories will be based on the number of participants with no missing data (i.e., will add up to 100%).

Baseline will be defined as the last nonmissing observation prior to first administration of IP, unless otherwise specified.

Demographics and baseline characteristics (age, sex, race, ethnicity, body weight, height and BMI) will be summarized by treatment group and overall for all randomized participants.

The number and percentage of participants who completed and discontinued treatment and reasons for treatment discontinuation will be presented for all randomized participants and for participants in the safety analysis set (SAF) by treatment group (ASP8062 alone, placebo alone, morphine in combination with ASP8062, morphine in combination with placebo) and overall. Similar tables for screening disposition, investigational period disposition and follow-up disposition will also be presented for all randomized participants by treatment group (ASP8062 alone, placebo alone, morphine in combination with ASP8062, morphine in combination with placebo) and overall. All disposition details and dates of first and last evaluations for each participant will be listed.

Previous and concomitant treatment (medication and nonmedication therapy) and medical history will be listed. The number and percentage of participants exposed to IP will be summarized by treatment group (ASP8062 alone, placebo alone, morphine in combination with ASP8062, morphine in combination with placebo) and visit. All IP exposure data will be listed.

9.4.2 Analysis of Efficacy

Not applicable.

9.4.3 Analysis of Safety

For analysis of safety, the treatment groups are (ASP8062 alone, placebo alone, morphine in combination with ASP8062, morphine in combination with placebo).

9.4.3.1 Adverse Events

AEs will be coded using MedDRA. An AE with onset at any time from first dosing until last scheduled procedure will be classified as a treatment-emergent adverse event (TEAE) for inclusion in the summary tabulations. An IP-related TEAE is defined as any TEAE with a causal relationship assessed as “yes” by the investigator, or records where the relationship is missing.

An overview and separate summaries of the number and percentage of participants with TEAEs, IP-related TEAEs, TEAEs leading to withdrawal of treatment, IP-related TEAEs leading to withdrawal of treatment and TEAEs excluding SAEs that equal or exceed a threshold of 5% in any treatment group will be presented by SOC, preferred term and treatment group. Also included in the overview are the number and percentage of participants with serious TEAEs, IP-related serious TEAEs, TEAEs leading to death and IP-related TEAEs leading to death.

The number and percentage of participants who have a TEAE within the drug abuse dependence Standardized MedDRA Queries (SMQ) (MedDRA v22.0) as classified by SOC

and preferred term, will be summarized by treatment group. In addition, the number and percentage of participants who have drug abuse-related TEAEs as classified by preferred term and lowest level term will be summarized by treatment group [Section 10.10 Appendix 10 Adverse Events of Interest Related to Potential Substance Abuse and Following Drug Withdrawal].

The number and percentage of participants who have a TEAE with the drug withdrawal SMQ (MedDRA v22.0) as classified by SOC and preferred term will be summarized by treatment group. In addition, the number and percentages of participants who have withdrawal-related TEAEs as classified by SOC and preferred term will be summarized by treatment group [Section 10.10 Appendix 10 Adverse Events of Interest Related to Potential Substance Abuse and Following Drug Withdrawal].

AE data will be listed.

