Treatment Groups and Duration: 

Arm/IP Name	ASP8062	Placebo ASP8062	Morphine sulfate	

Use	Test product	Placebo for ASP8062	Test product	

Dose	25 mg (1 × 25 mg tablet)	NA (1 × tablet)	45 mg (3 × 15 mg immediate-release tablets)	

Frequency	Once daily	Once daily	Single dose	

Route	Oral	Oral	Oral	

Duration	10 days	10 days	1 day	

 IP: investigational product; NA: not applicable The anticipated duration of the study for each participant, including screening and follow-up, is approximately 53 days.	Arm/IP Name	ASP8062	Placebo ASP8062	Morphine sulfate	Use	Test product	Placebo for ASP8062	Test product	Dose	25 mg (1 × 25 mg tablet)	NA (1 × tablet)	45 mg (3 × 15 mg immediate-release tablets)	Frequency	Once daily	Once daily	Single dose	Route	Oral	Oral	Oral	Duration	10 days	10 days	1 day
Arm/IP Name	ASP8062	Placebo ASP8062	Morphine sulfate																					
Use	Test product	Placebo for ASP8062	Test product																					
Dose	25 mg (1 × 25 mg tablet)	NA (1 × tablet)	45 mg (3 × 15 mg immediate-release tablets)																					
Frequency	Once daily	Once daily	Single dose																					
Route	Oral	Oral	Oral																					
Duration	10 days	10 days	1 day																					

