4 STUDY DESIGN AND DOSE RATIONALE

4.1 Overall Study Design

This will be a randomized, participant- and investigator-blinded, placebo-controlled, single sequence study comprising of male and female recreational opioid-using participants.

Approximately 24 male and female participants will be randomly assigned to complete at least 18 participants. An attempt will be made to enroll 1 female participant for every 3 male participants. The study will be conducted at 1 study site in the US.

Participants will be screened for up to 28 days prior to first investigational product (IP) administration. Eligible participants will be admitted to the clinical unit on day -1 and will be residential for a single period of 17 days/16 nights. After randomization, participants will receive multiple oral doses of ASP8062 or placebo (2:1 ratio) on days 1 through 10. On day 10, all participants will also receive a single oral dose of morphine immediately after the ASP8062 or placebo dose followed by a 144-hour in-house blood sampling period.

Scheduled safety and tolerability assessments will be conducted as indicated in the Schedule of Assessments [Table 1]. Participants are to remain awake, seated or semirecumbent and avoid lying on either the left or right side for at least 4 hours postdose on days 9 and 10.

Participants will be discharged from the clinical unit on day 16 on the condition that all required assessments have been performed and that there are no medical reasons for a longer stay in the clinical unit.

The study will be completed with an end-of-study visit (ESV). The ESV will take place 5 to 9 days after the day 16 pharmacokinetic sample is collected or at early discontinuation/termination from the study.

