9.4.3.3 Vital Signs

Descriptive statistics will be used to summarize vital sign results (blood pressure, pulse and respiratory rate) and changes from baseline for participants in the SAF by treatment group and time point.

The number and percentage of participants with respiratory rate values as per Table 7 at any time point will be summarized by treatment group. The lowest and highest respiratory rate, respectively, will be used in the analysis.

Table 7 Criteria for Respiratory Rate

Vital Sign	Criteria
Respiratory Rate (breaths/minute)	< 6, < 8, < 10 > 24, > 28, > 32, > 36

The number and percentage of participants who reach an alarm value for the continuous respiratory rate, and the number of times an alarm value was reached will be listed and summarized by treatment.

Vital signs data will be listed.

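### TEAE percentages and worst respiratory-rate counts compare alone and combination columns over unequal, unstated windows (9 versus 11 to 15 days; 9 versus 12 readings); add matched day 9 and day 10 tables

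*Combined protocol and SAP*

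**What the plan says.** The primary objective (Section 3, Table 3) covers safety of ASP8062 or placebo both by itself and together with one morphine dose. Section 9.4.3 sets the columns accordingly: "the treatment groups are (ASP8062 alone, placebo alone, morphine in combination with ASP8062, morphine in combination with placebo". Each participant who reaches day 10 therefore contributes to one alone column and one combination column.

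The schedule is in Section 4.1. The blinded tablets continue up to and including the morphine day: "participants will receive multiple oral doses of ASP8062 or placebo (2:1 ratio) on days 1 through 10". Morphine comes only once, at the end of that course: "On day 10, all participants will also receive a single oral dose of morphine immediately after the ASP8062 or placebo dose". The final visit is timed from the last inpatient sample: "The ESV will take place 5 to 9 days after the day 16 pharmacokinetic sample is collected".

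Two summaries matter here.

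- **TEAEs (Section 9.4.3.1).** "An AE with onset at any time from first dosing until last scheduled procedure will be classified as a treatment-emergent adverse event". Results are numbers and percentages of participants by treatment group. No rate per unit of time is planned.
- **Respiratory rate (Section 9.4.3.3).** Participants crossing a Table 7 threshold at any time point are counted by treatment group: "The lowest and highest respiratory rate, respectively, will be used in the analysis". The same section also summarises respiratory rate and its change from baseline by group and time point.

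Neither section says which column takes an AE onset or a reading, for example the day 10 predose vital signs.

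**The concern.** The natural use of the four columns is to read across from alone to combination within an arm and attribute the change to morphine. That reading needs comparable periods of observation. Here one column covers the run-in, and the other covers the morphine day plus washout and follow-up. A percentage of participants with any event, and a worst value over all readings, both tend to rise with the length of observation, whatever drug was given.

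Content differs as well as length. Section 9.4.3.1 tabulates withdrawal-related TEAEs in the same columns, and events caused by stopping ASP8062 after day 10 can fall only under combination. Nausea and vomiting are withdrawal terms in Appendix 10 and also morphine events of special interest in Section 7.3.6, so the full-period column cannot separate the two sources.

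The groups are small. About 24 participants at 2:1 is 16 and 8, so one participant is 6.25% or 12.5% and a single late background event can change a table.

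**Working it through.** **1. Check that the schedule was read correctly.** The Synopsis states: "The anticipated duration of the study for each participant, including screening and follow-up, is approximately 53 days". Screening 28 + days 1 to 16 + latest ESV 9 = 53, which agrees. Counting the Table 2 rows gives 16 laboratory draws, 13 + 13 + 8 + 1 = 35 ASP8062 samples and 11 + 3 = 14 morphine samples, all equal to Table 6.

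**2. AE windows, split at the day 10 dose.**
- Alone: 10 − 1 = 9 days.
- Combination: from 16 + 5 − 10 = 11 to 16 + 9 − 10 = 15 days.

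**3. Respiratory-rate readings (Table 2).** Day 1 predose is excluded as baseline (Section 9.4.1).
- Alone: days 3 and 6 (2), day 9 predose and 1, 2, 4, 8, 12 h (6), day 10 predose (1) = 9.
- Combination: day 10 at 1, 2, 4, 8, 12 h (5), then 24, 48, 72, 96, 120, 144 h (6), ESV (1) = 12. Seven of the 12 are at 24 h or later.
- If day 10 predose were placed under combination: 8 versus 13.

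**4. AEs with no morphine effect.** The documents give no background rate, so the rates are assumptions. With p the incidence in 9 days and a constant daily rate, incidence in d days is 1 − (1 − p)^(d/9).

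| 9 days | 11 days | 15 days | Extra participants of 16 |
|---|---|---|---|
| 10% | 12.1% | 16.1% | 0.3 to 1.0 |
| 30% | 35.3% | 44.8% | 0.9 to 2.4 |
| 50% | 57.1% | 68.5% | 1.1 to 3.0 |

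The excess disappears when the later daily rate falls to 9/11 = 0.82 of the earlier one (11-day window) or 9/15 = 0.60 (15-day window), and reverses below that. As an extreme assumption, if nothing were captured after discharge on day 16 (6 days), 30% would become 1 − 0.7^(6/9) = 21%.

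**5. Worst respiratory rate with no morphine effect.**
- Independent readings, assumed mean 15 and SD 2.5, whole-number recording: q = Φ((9.5 − 15)/2.5) = Φ(−2.2) = 0.0139. The chance of any value below 10 is 1 − (1 − q)^m: 11.8% for m = 9, 15.5% for m = 12.
- Correlated readings: beta-binomial with within-participant correlation ρ = 0.3, a = q(1/ρ − 1), b = (1 − q)(1/ρ − 1), probability 1 − B(a, b + m)/B(a, b). At q = 2%: 8.0% versus 9.0%. At q = 5%: 18.9% versus 21.2%.

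**6. Dilution of the randomized comparison.** Let b be late background incidence, equal in both arms and independent of early events. An early difference Δ in any-TEAE incidence becomes Δ(1 − b). At the 30%-per-9-days rate, 10 to 14 late days give b = 1 − 0.7^(10/9) = 33% to 1 − 0.7^(14/9) = 43%. A 30-point difference then shrinks to about 20 to 17 points. Single preferred terms are diluted less.

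**7. Matched windows.** With the five postdose readings on each day (m = 5), the chance in step 5 under independence is 6.8% on both days, so the length-driven gap is zero. Equal 24 h windows do the same for AEs.

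**The case against.** A reader might infer that the combination columns will look worse by construction even if morphine does nothing. The documents do not support that. The alone window holds nine of the ten dosing days. The combination window holds one, then washout, and after discharge on day 16 the 5 to 9 outpatient days have a single scheduled contact. If AEs cluster around dosing, or are captured less fully after discharge, the bias shrinks or changes sign. For respiratory rate, repeated readings in one person are unlikely to be independent, and the gap is then slight.

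The rest of the defence is also substantial:

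- The windows are inferred from the schedule; the plan never states them.
- Respiratory rate is already summarised by time point, so day 9 and day 10 values at the same hours will be visible. Only the threshold count is unmatched.
- Continuous monitoring covers the same hours on days 9 and 10. Spot end tidal CO2 has four postdose readings on each day. Spot SpO2 is 6 versus 6, or 7 versus 5, leaning the other way, if day 10 predose counts as alone.
- Section 2.1 names the particular target as an additive effect of ASP8062 on top of morphine. Those two randomized columns have identical windows.
- Sections 9.1 and 9.2 set no hypotheses and no power, so no test is invalidated.
- Late events are not mere background: the ASP8062 half-life of about 60 hours (Section 4.2) puts five half-lives at 12.5 days, and morphine is sampled to 48 h.

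All of this stands against a claim of fixed direction or large size, and against demoting the full-period tables. It does not make the alone-versus-combination contrast interpretable: a bias of unknown sign is still a bias, and the missing assignment rule remains missing.

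**Conclusion.** The concern holds in a limited form. TEAE percentages and Table 7 counts compare columns that cover unequal periods, under a split the plan implies but does not state, with no adjustment. The descriptive alone-versus-combination contrast is therefore confounded with window length.

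The size depends on assumptions the documents cannot settle. AEs carry the larger potential distortion, about one to two and a half participants of 16 at a constant rate and 30% incidence, but its sign is not fixed. The respiratory-rate distortion is a few points at most under the assumptions used. The randomized comparison after morphine is unbiased and can only be diluted. This is a cheap improvement to reporting, not a flaw in the design.

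**What to change.** In Sections 9.4.3.1 and 9.4.3.3, keep the full-period tables at their present standing, because multiple-dose tolerability and withdrawal-related TEAEs need them. Add, by randomized arm:

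1. TEAEs with onset within 24 h after the day 9 dose, beside those with onset within 24 h after the day 10 dose.
2. Table 7 counts using the lowest and highest respiratory rate among the 1, 2, 4, 8 and 12 h readings on day 9, beside the same five on day 10.

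State in Section 9.4.3 that onsets before the day 10 dose, and day 10 predose readings, belong to alone.

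The cost is a few extra tables and one sentence, with no new data collection; Table 2 already schedules the same postdose vital-sign times on both days. The drawback is few events in a 24 h window, so the matched tables should be read with the full-period ones.
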